7.3. Full Analysis Set (FAS), Immunogenicity

FAS-1: Booster immunogenicity analysis

All subjects in the Enrolled Set who receive at least one booster dose during the trial (because RVNA value below 0.5 IU/mL at scheduled visit) or before entering the trial (e.g. travellers to endemic areas or veterinarians who got the booster regardless of the RVNA value) and provide immunogenicity data.

FAS-2: Long term immunogenicity analysis

All subjects in the Enrolled Set who provide immunogenicity data.

Note: In the long-term immunogenicity analysis, when a subject receives a rabies vaccine booster dose (before or during the study) because RVNA value is below 0.5 IU/mL, subsequent RVNA values after the booster dose will be set to half of the detection level (i.e. 0.1 IU/mL) until study end even if the subject withdraws earlier than last study visit (see last part of section [8.2](#) for a detailed explanation).

In case a subject receives a booster dose before or after entering the study (e.g. travellers to endemic areas, veterinarians) but the last known RVNA value was above 0.5 IU/mL, then he/she will be excluded from the long term immunogenicity analysis set (i.e. FAS-2 and PPS). This is justified by the fact that including actual values as recorded after the booster dose would inflate the immunogenicity persistence; on the other hand, it would be inappropriate to apply the same rule used for subjects receiving a booster dose when RVNA value is less than 0.5 IU/mL as this is not the case.

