8.2.2. Immunogenicity Data

Immune response in subjects with or without booster will exclude missing values, assuming missing immunogenicity values as Missing Completely At Random (MCAR) and therefore will not contain information that impact the result of the analysis (i.e., not informative).

Imputation methods will be used for those subjects who will receive a booster dose during the trial i.e., once the RVNA concentration fall below the predefine cut-off of 0.5 IU/mL, that value will be set up to half of quantification level from that moment onward.

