All further subject immunogenicity data will not be used for Time to event analysis.

GMC and percentage analysis - boostability:

Subject is included in the Exposed to Booster Set and independently on time or visit in which booster is administered the time-points will be as following:

- Pre-booster
- 7 days after booster
- 6 to 9 months after booster

Long-term persistence of antibody responses after primary series

All immunogenicity data until booster will be part of analysis as they are reported.

For subjects receiving a booster dose, the following method of imputation will be used for antibody values:

- Values, missing or not, will be replaced with half of the quantification level (0.1 IU/mL) from that moment onward.

Subjects receiving a booster dose outside of the study and for which RVNA value at the time of booster vaccination is not available will be excluded from FAS-2 and PPS-2 (see section 7.3 for details)

Duration in the Study

Duration in the study is defined in days as:

Last visit date (visit x)^a – Enrollment date (visit 1) + 1

^a or premature discontinuation date (in case of withdrawal from the study)

The duration is missing if one of the dates is missing or incomplete.

Unsolicited Serious Adverse Events

All serious adverse events (AEs) following *Rabipur* booster dose within the study will be characterized according to the date of occurrence related to the vaccination phase as follows:

- **Emergence before vaccination phase:** start date before the first date of injection of study vaccine.
- **Emergence during vaccination phase:** start date on or after the first date of injection of study vaccine or, adverse event increase in severity including to “serious” AE.

If start date is equal to the first date of injection then “timing” variable (“On injection day, before injection”/“On injection day, after injection”) will be used to define whether the adverse event occur before or after the injection.

If an AE start date is missing or unknown, the AE will be considered as emergent.

When start and/or end dates of an AE are only partially known, AEs will be categorized as emergent before, during, or after vaccination phase using the following rules:

- If the partial end date is before ($<$) the first study vaccination (i.e., year or year & month is/are before the first study vaccination year or year & month) then the AE is emergent before vaccination phase.

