10.1. Demographics

As demographic characteristics the following variables will be summarized by reporting the mean, standard deviation, median and range, and will be calculated by vaccine group and overall:

- Age at time of first exposure (i.e., enrolment in study V49_23).
- Height, weight, and BMI at time of extension study enrolment (i.e., enrolment in V49_23E1)

The frequencies and percentages of subjects by sex, country, age categories (for posting), race, entry criteria fulfilled and booster received before entering in to the study V49_23E1 will be presented by vaccine group and overall.

Demographic data will be tabulated for the All Enrolled subjects, for Exposed to Booster dose set and for FAS-2.

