11.3. Secondary Objectives Analysis

Secondary Immunogenicity Objective:

To evaluate the long-term (up to approx.10 years) immunogenicity in subjects who received a primary series of accelerated or conventional rabies PrEP intramuscular (IM) regimen in the parent study V49_23.

Yearly Geometric Mean Concentrations up to Year 10

All subjects enrolled in this extension study, independently from booster administration, are planned to be followed until year 10 from the primary vaccination.

Log-transformed antibody titers as collected at annual Scheduled Clinic Visits (from Visit 1 to Visit 7) will be analyzed using a mixed model for repeated measures within subject, including time, center and treatment as independent variables, interaction for time and treatment, a random intercept with an unstructured covariance matrix.

SAS code will look like the following:

```
PROC MIXED DATA = model;
  class subject time treatment center;
  model log_Ab = time treatment time*treatment center/ CL s ;
  lsmeans time treatment time*treatment;
  random intercept / subject = usubjid type = UN;
RUN;
```

Reverse Cumulative Distribution Figure (RCDF) up to Year 10

The percentages of subjects with concentration greater than or equal to defined RVNA values (on log10 scale) will be presented as reverse cumulative distribution curve, having the individual RVNA concentration on the X-axis and the percentage of subject with equal to or greater than the value on the Y-axis by each study visit (i.e., Year)

Note: If subject receives a booster during the study, for the purpose of the secondary objective analysis on long-term persistence of immune responses the RVNA concentration after the booster will not be 'entered' as such, but half of quantification level from that moment will be used for all consecutive visits.

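### SAP 7.3 and 8.8 test subjects boosted outside the study differently for FAS-2; read literally, 8.8 drops some who were already seen below 0.5 IU/mL

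*SAP*

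**What the plan says.** The note to FAS-2 in SAP 7.3 contains a keep rule and an exclusion rule. The keep rule applies "when a subject receives a rabies vaccine booster dose (before or during the study) because RVNA value is below 0.5 IU/mL": the subject stays in the set, and every later value is replaced by 0.1 IU/mL to the end of the study. The exclusion rule applies to a subject boosted before or after entry "but the last known RVNA value was above 0.5 IU/mL, then he/she will be excluded from the long term immunogenicity analysis set".

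SAP 8.8, in its text on imputation after a booster, adds a third rule. It removes from FAS-2 and PPS-2 "Subjects receiving a booster dose outside of the study and for which RVNA value at the time of booster vaccination is not available", and refers the reader to 7.3.

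The scope of the imputation is also worded unevenly. SAP 7.3 covers boosters before and during the study, and the imputation sentences in 8.2 and 8.8 carry no limit. SAP 8.2.2 says "Imputation methods will be used for those subjects who will receive a booster dose during the trial", and the note in 11.3 begins "If subject receives a booster during the study, for the purpose of the secondary objective analysis on long-term persistence".

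The plan expects outside boosters. SAP 10.1 tabulates "booster received before entering in to the study V49_23E1", 7.3 admits such subjects to FAS-1, and 8.8 defines a time-point code for a booster given between the two studies.

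**The concern.** The two sections look at different readings. SAP 7.3 asks what the last known value was. SAP 8.8 asks whether a value exists at the moment of the booster. The study draws no sample when a booster is given elsewhere, so that value will often be missing, and 8.8 makes no exception for a subject whose last reading was already below the threshold.

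A subject below 0.5 IU/mL at parent-study Day 366, or at an annual visit, and then boosted elsewhere because of it, is a documented waning failure. Under 7.3 that failure stays in the long-term summaries. Under the literal wording of 8.8 the subject leaves the set. That exclusion depends on the outcome being summarised, and from the drop onward it works in one direction. The yearly GMCs, the percentages at or above 0.5 IU/mL and the reverse cumulative curves then depend on which section is programmed.

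**Working it through.** **Comparing the rules.** For a booster given outside the study:

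| Case | Last reading before booster | Reading at booster | SAP 7.3 | SAP 8.8, literal | Result |
|---|---|---|---|---|---|
| a | above 0.5 | none | excluded | excluded | agree |
| b | below 0.5, boosted because of it | available, below 0.5 | kept, 0.1 imputed | not excluded | agree |
| c | below 0.5, boosted because of it | none | kept, 0.1 imputed | excluded | conflict |
| d | below 0.5, boosted for another reason (e.g. travel) | none | neither sentence applies | excluded | gap in 7.3 |

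SAP 7.3 already removes case a. What 8.8 adds is therefore cases c and d, plus the rare subject with a reading of exactly 0.5 or with no reading at all. The added exclusions fall almost wholly on observed failures.

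**In-trial boosters.** SAP Table 3 schedules no blood draw at the Ad hoc (booster) visit, and SAP 11.2 takes the Scheduled Visit reading about six months earlier as the pre-booster value. For an in-trial booster an earlier reading is good enough; for an outside booster, literal 8.8 does not accept one.

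**Size.** The plan gives no figure to reproduce and no count of affected subjects. Inputs:
- N = 209, the maximum for Acc-R/JE (SAP Table 1).
- k = 2 or 5 deleted failures (assumed).
- True percentage at or above 0.5 IU/mL of 40% or 80% (assumed), giving a = 84 or 167 subjects.
- Floor of 0.1 IU/mL (SAP 7.3 and 8.8).
- G, the GMC of the remaining subjects, 0.5 to 2 IU/mL (assumed).

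The percentage is a/N if failures are kept and a/(N − k) if they are deleted:
- k = 2: 84/209 = 40.2% becomes 84/207 = 40.6% (+0.4 points); 167/209 = 79.9% becomes 167/207 = 80.7% (+0.8).
- k = 5: 84/204 = 41.2% (+1.0); 167/204 = 81.9% (+2.0).

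The simple GMC is G^((N − k)/N) × 0.1^(k/N) with failures kept and G with them deleted, a ratio of (G/0.1)^(k/N):
- k = 2: 5^(2/209) = 1.02 to 20^(2/209) = 1.03.
- k = 5: 5^(5/209) = 1.04 to 20^(5/209) = 1.07.

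The model-based means in SAP 11.3 will differ somewhat from these simple GMCs.

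**Direction.** a/(N − k) exceeds a/N for any k above 0 (with a above 0), and the GMC ratio exceeds 1 whenever G is above 0.1. For a subject boosted between the studies this applies at every extension visit. For a subject whose drop came during the extension, deletion also removes the earlier values at or above 0.5, so the upward direction applies from the visit of the drop onward.

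**The case against.** The strongest reply is that 8.8 cites 7.3, so 7.3 governs, and that the documents use booster-time language loosely. Protocol 8.4.2.3.3 takes the value at the booster visit as baseline although no sample is scheduled there, and SAP 11.2 uses the previous Scheduled Visit reading. If 8.8 also means the last known value, the conflict disappears. That reading is possible, but it leaves 8.8 almost nothing to do: entrants completed a parent study with readings up to Day 366, so nearly all have a last known value. The literal reading, in turn, nearly empties the pre-entry part of the 7.3 keep rule. The SAP does not choose between them.

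The reply also limits the point. A reader might infer four stronger claims that the documents do not support:
- **That 7.3 keeps, and 8.8 deletes, every subject last seen below 0.5 and boosted elsewhere.** The 7.3 keep rule needs a booster given because of the low value, and 8.8 acts only when no value at booster is available.
- **That such a subject could be scored as protected, using real post-booster values, under 8.2.2 and 11.3.** Neither section says so. SAP 8.2 and 8.8 impute without a during-study limit, and 7.3 rejects actual post-booster values because they would inflate persistence.
- **That the primary time-to-event result is biased.** SAP 8.8 scores an observed value below 0.5 as an event, and censors rather than deletes boosted subjects whose value is unknown. The SAP does not clearly tie that analysis to FAS-2. Protocol 8.4.2.3.2 names the All Enrolled Set and FAS-1 for the primary objective, and 8.4.3.3.2 names FAS-2 for the secondary.
- **That the accelerated arm gains more.** SAP 11.2 reports a difference between schedules at Day 366 but gives no direction or size.

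Numbers may also be small. Protocol 4.2 lists non-study rabies vaccine among the exclusions checked before Scheduled Visits.

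**Conclusion.** The inconsistency is real and affects the long-term summaries on FAS-2. SAP 7.3 and 8.8 give opposite results for a subject boosted outside the study because of a reading below 0.5 IU/mL with no reading at booster. A subject last seen below 0.5 and boosted for another reason is covered by neither 7.3 sentence. Under literal 8.8 both are removed, which favours apparent persistence from the drop onward.

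The size is illustrative only. With the Acc-R/JE maximum of 209 and an assumed 2 to 5 such subjects, the percentage at or above 0.5 IU/mL rises by about 0.4 to 2.0 points and the simple GMC by about 2% to 7%. Both ranges rest on the assumed counts and levels, since the documents give no number of affected subjects. The primary time-to-event analysis is not shown to be affected. The correction is still worth making because it removes an outcome-dependent exclusion at little cost.

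**What to change.** In SAP 8.8, replace the condition about availability of a value at booster with one test based on the last known reading, and word 7.3 to match:

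- For any booster outside the study, take the last RVNA reading after the primary series, from the parent or the extension study, before that booster, whatever prompted the booster.
- If it is below 0.5 IU/mL, keep the subject in FAS-2 and apply the SAP's post-booster imputation.
- If it is 0.5 IU/mL or higher, or no reading exists, exclude the subject from FAS-2. This also settles a reading of exactly 0.5, which the 7.3 exclusion sentence leaves out.
- In 8.2.2 and 11.3, extend the imputation to boosters before as well as during the study, as 7.3 has it.

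Two things should stay as they are. The survival event remains at the first reading below 0.5, which may precede the last reading before the booster. PPS-2 membership remains with the existing Table 5 codes 2010 (eligibility) and 2040 (prohibited vaccination), so keeping a subject in FAS-2 does not override those exclusions.

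It would also help to name the analysis set for the survival analysis and to report the affected subjects by arm. The cost is SAP wording and one programming condition, with no new data. The downside for the sponsor is that persistence figures may become slightly less favourable.

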8.9. Analysis Software

All analyses will be performed using SAS Software version 9.2 or higher.

9. STUDY SUBJECTS

9.1. Disposition of Subjects and Withdrawals

All subjects who successfully completed rabies PrEP regimens in V49_23 and did not have protocol deviations which can impact the immunogenicity response (e.g., wrong vaccination), and who provide informed consent will be accounted for in this study. The frequencies and percentages of subjects in each analysis set, study withdrawals, and protocol deviations will also be presented.

For the purpose of the IA subject disposition will be summarized for the three following analysis sets: from All enrolled set to FAS-2 set, from FAS-2 set to PPS-2 set and eligible for booster dose to exposed to booster dose set.

The time the subjects are under observation will be summarized by vaccine group and overall using summary statistics (mean, SD, minimum, median, maximum)

10. DEMOGRAPHICS AND OTHER BASELINE CHARACTERISTICS

In general, all tables presented in CSR section 14.1 should show a Total column across vaccine groups.

10.1. Demographics

As demographic characteristics the following variables will be summarized by reporting the mean, standard deviation, median and range, and will be calculated by vaccine group and overall:

- Age at time of first exposure (i.e., enrolment in study V49_23).
- Height, weight, and BMI at time of extension study enrolment (i.e., enrolment in V49_23E1)

The frequencies and percentages of subjects by sex, country, age categories (for posting), race, entry criteria fulfilled and booster received before entering in to the study V49_23E1 will be presented by vaccine group and overall.

Demographic data will be tabulated for the All Enrolled subjects, for Exposed to Booster dose set and for FAS-2.

10.2. Medical History

The frequencies and percentages of subjects with medical history will be presented by MedDRA system organ class and PT, and by vaccine group and overall. Medical history data will be tabulated for the All Enrolled Set.

11. IMMUNOGENICITY ANALYSIS

11.1. Blood Samples

The frequencies and percentages of subjects with blood draws will be summarized overall and by vaccine group. Data will be tabulated for the All Enrolled set.

11.2. Primary Objectives Analysis

Primary Immunogenicity Objectives:

1. To compare the long-term (up to approx.10 years) persistence of antibody responses (i.e. time until antibody concentrations drop below 0.5 IU/mL) in subjects who received a primary series of accelerated or conventional rabies PrEP intramuscular (IM) regimen in the parent study V49_23.
2. To evaluate the antibody responses to a booster dose of Purified Chick Embryo Cell-Culture (PCEC) rabies vaccine administered to subjects with Rabies Virus Neutralizing Antibody (RVNA) concentrations < 0.5 IU/mL following a primary series of accelerated or conventional rabies PrEP IM regimen in the parent study V49_23.

Primary hypotheses:

There is no null hypothesis associated to primary objectives.

Time to first RVNA concentrations < 0.5 IU/mL

Cox proportional hazards regression model

Since, already at the end of the parent study (Day 366, study V49_23) it was observed a difference in the persistence of adequate RVNA concentrations between subjects who have received the accelerated PrEP schedule and those who received the conventional rabies vaccines schedule, the HR from the Cox proportional hazards regression model will be used as a treatment effect measure for time to event endpoints.

Statistical model:

An adjusted proportional hazards regression Cox model will be used:

$$h(t) = h_0(t) \cdot \exp(\beta_1 x_1 + \beta_2 x_2)$$

where:

t represents the survival time

$h(t)$ is the hazard function as determined by the covariates treatment and center

$h_0(t)$ is the baseline hazard function at time t

X_1 represents treatment

X_2 represents center

β_1 and β_2 are the unknown parameters for treatment and center, to be estimated.

The HR is a multiplicative constant $\exp(\beta_1)$ comparing the hazard function in the accelerated schedule group relative to the hazard function in the conventional schedule group.

The HR will be derived from the Cox proportional hazards model using SAS PROC PHREG (with TIES=EXACT).

HR point estimate(s) will be based on partial maximum likelihood function, and Wald-test based two-sided 95% confidence intervals will be requested by the RISKLIMITS option.

The following SAS code will be applied:

```
PROC PHREG data=<dataset>;
  class arm center;
  MODEL survtime*status(0)=ARM center/ TIES=EXACT RISKLIMITS;
  RUN;
```

survtime represents variable containing event/censoring times.

status represents censoring variable (0=censored, 1=event).

Estimation of survival functions

The term “survival function” $S(t)$ is used here in its general meaning as probability of experiencing a specific event at time t or later. The event of interest is the time when **RVNA concentrations < 0.5 IU/mL**.

A graphical estimate of the survival function separately for each vaccine schedule group will be obtained by the KM product - limit method as implemented in SAS PROC LIFETEST.

Together with the KM curve, the 95% CIs, will be estimated and displayed per each vaccination regimen. Standard errors of the KM estimates will be based on the Greenwood’s method; 25th and 75th percentile and median survival will be provided if estimable.

Data will include observations at 7 days after primary vaccine schedule and at 3, 5 and 12 months from the parent study (V49_23) and the year observations from this study.

```
PROC LIFETEST data=<dataset> plots=(survival(atrisk) logsurv);  
TIME survtime*Status(0);  
STRATA arm;  
RUN;
```

Immune response to booster dose

Geometric Mean Concentration and Geometric Mean Ratios (GMR)

For subjects receiving a booster dose, analysis of boostability will be conducted 7 days and 6 months after administration of the booster dose by providing GMRs and associated 95% CIs, considering the antibody value before the booster visit (i.e., 6 months before following the blood drawn during previous Scheduled Clinic Visit) as baseline (denominator) and the antibody concentration at 7 days and at 6 months after booster as the numerator.

Independently of the time (i.e., visit) a subject receives a booster dose of PCEC vaccine, RVNA concentration as detected from the blood drawn during previous scheduled clinic visit (approximately six months before the booster administration) will be considered baseline value and summarized by the mean of GMC, with associated 95% CIs, median, minimal and maximal values for each vaccine schedule group. In the same table the 7 days and 6 months post booster dose response and geometric mean ratio will be described. ***Percentage of subjects with RVNA concentrations ≥ 0.5 IU/mL***

No inferential model is defined for the binomial variable (i.e., subject with RVNA concentrations ≥ 0.5 IU/mL). Percentages of subjects at 7 days and at 6 months (i.e., at subsequent Scheduled Clinical Visit) after the booster dose will be presented together with 95% CIs (Clopper, 1934) by primary vaccine schedule (arm).

11.3. Secondary Objectives Analysis

Secondary Immunogenicity Objective:

To evaluate the long-term (up to approx.10 years) immunogenicity in subjects who received a primary series of accelerated or conventional rabies PrEP intramuscular (IM) regimen in the parent study V49_23.

Yearly Geometric Mean Concentrations up to Year 10

All subjects enrolled in this extension study, independently from booster administration, are planned to be followed until year 10 from the primary vaccination.

Log-transformed antibody titers as collected at annual Scheduled Clinic Visits (from Visit 1 to Visit 7) will be analyzed using a mixed model for repeated measures within subject, including time, center and treatment as independent variables, interaction for time and treatment, a random intercept with an unstructured covariance matrix.

SAS code will look like the following:

```
PROC MIXED DATA = model;
  class subject time treatment center;
  model log_Ab = time treatment time*treatment center/ CL s ;
  lsmeans time treatment time*treatment;
  random intercept / subject = usubjid type = UN;
RUN;
```

Reverse Cumulative Distribution Figure (RCDF) up to Year 10

The percentages of subjects with concentration greater than or equal to defined RVNA values (on log10 scale) will be presented as reverse cumulative distribution curve, having the individual RVNA concentration on the X-axis and the percentage of subject with equal to or greater than the value on the Y-axis by each study visit (i.e., Year)

Note: If subject receives a booster during the study, for the purpose of the secondary objective analysis on long-term persistence of immune responses the RVNA concentration after the booster will not be 'entered' as such, but half of quantification level from that moment will be used for all consecutive visits.

